1.3 Study Rationale

1.3.1 Preclinical experience on CDK4/6 inhibition and DCIS

Loss of the retinoblastoma tumor suppressor pathway (Rb) is one of the strongest markers of DCIS recurrence and progression. Preclinical studies support the development of Cdk 4/6 inhibitors in DCIS. Cdk4 and Cdk6 are very important in cellular proliferation; they phosphorylate Rb and initiate transition from the G1 phase to the S phase in the cell cycle. Inhibition of Cdk4 and Cdk6 activity in an Rb-dependent manner prevents the development of invasion lesions⁴³. Furthermore, immortal mammary epithelial cell lines with Rb knockout lead to invasive lesions in xenograft assays but Rb proficient parental cells lead to DCIS-like lesions⁴³.

In our hands, the well-established MCF-DCIS in vitro model gives well defined DCIS lesions when implanted subcutaneously in animals. These lesions progress to invasive disease within 3-5 weeks in this model^{44,45}. Pathologic features and gene expression pattern of MCF-DCIS mimics that of human DCIS lesions⁴⁶. The ductal lesions that develop after 3 weeks implantation of MCF-DCIS cells resemble high grade comedo DCIS and both the luminal and myoepithelial cell layers of the DCIS lesions are derived from the progenitor MCF-DCIS cells^{45,47}. We determined that palbociclib can inhibit MCF-DCIS proliferation in vitro (Fig 1). The IC₅₀ was approximately 100 nM, at which concentration there was significant change in morphology of the cells. We also observed a significant decrease in Cdk2 and PCNA expression in the cells with low

doses of palbociclib treatment. In Matrigel™ model, MCF-DCIS cells grow into multiacinar structures (**Fig 2**). When exposed to palbociclib 0.1 μ M for 7 days, there was significant change in laminin V distribution to the periphery of the acini and a more normal steroid acinar structure was observed (**Fig 2d**).

In previous xenograft studies at our center, with an Rb-dependent mammary gland dysplasia mouse model *Tet-op-TAg^{MMTV-tTA}*, 10 days of exposure to Palbociclib significantly reduced the percentage of hyperplastic and dysplastic ductal structures [58% vs. 7%; p<0.01] and significantly increased the percentage of normal-like structures [9% vs. 62%; p<0.01] as compared with untreated controls⁴⁸. Cyclin D1, Cdk6, Cdk4, phospho pRb, DP-1, and E2F-1 were significantly reduced and p21 and p27 significantly increased as compared with untreated controls [all p<0.05]. Our preclinical results indicate that palbociclib may prevent maintenance of DCIS and its malignant progression.

Interrupting cancer development by inducing resolution of precancerous lesions is an established cancer prevention goal⁴⁹. Based on preclinical DCIS information and on clinical experience with palbociclib for patients with metastatic cancer, the concept of developing palbociclib as potential chemoprevention agent is felt to be very promising.

1.3.2 Palbociclib as potential treatment for DCIS

Nothing is known about the clinical or biological activity of palbociclib in human DCIS or early stage breast cancer. This project is designed to understand and describe palbociclib activity in humans, in particular in pre-invasive lesions such as DCIS, and to provide critical preliminary data supportive of future efficacy studies. For the design of efficacy clinical studies that would lead to potential new label indication, preliminary human data must be indicative of its potential clinical usefulness for this population of patients. That is the reason for the current study: to generate supportive information in humans that will allow the design of a larger efficacy study.

This study will validate the incorporation of an informative preoperative short treatment phase as potential strategy to select DCIS patients, a crucial step for the development of treatment with palbociclib in this condition.

Palbociclib as single agent: The current study will represent a unique opportunity to evaluate the potential effect of single agent palbociclib on non-invasive breast lesions. Preclinical models suggest that in DCIS, palbociclib single agent may be sufficient. Apart from strong evidence supporting the activity of palbociclib combined with endocrine therapy, multiple TNBC cell lines where endocrine therapy would have no role have been screened for sensitivity to palbociclib³⁸, revealing sensitivity of the luminal-androgen (LAR) and mesenchymal-stem like (MSL) triple negative subsets. In addition, palbociclib was active in the single agent phase IA escalation study A548100152, where 74 heavily pretreated patients with various types of solid tumors or lymphomas, including 6 patients with breast cancer, were treated. There was 35% SD for at least 2 cycles with one breast cancer patient receiving 50 mg QD with SD lasting longer than 10 cycles. Another reason to study single agent palbociclib in DCIS is that endocrine therapy is the only systemic treatment currently approved for DCIS. Endocrine therapy has well known potential side effects that may interfere significantly with quality of life of patients, including hot flashes, fluid retention, vaginal symptoms, thromboembolic complications, cataract, dyslipidemia, arthralgia, osteoporosis and uterine cancer^{50,51}. If palbociclib has biologic activity in DCIS as a single agent, this could represent a change in paradigm.

2. OBJECTIVES AND OUTCOME MEASURES

2.1 Hypothesis

The null hypothesis is that patients with DCIS of the breast who are treated with 12 days of pre-operative palbociclib will have no change in the gross DCIS pathology, microscopic morphology on H&E, or expression of phospho-Rb, Ki-67 proliferation, and multiple other biological markers of their cancer.

2.2 Objectives

2.2.1 Primary Objectives

- Feasibility
- Preliminary evidence of DCIS response to palbociclib: Pathologic changes of breast tissue comparing paired biopsies before and after treatment (core vs definitive surgery) from each patient.
 - Gross path, H&E changes, multiple biological markers (potentially including CDK4 and CDK6 expression, Cyclin D1 expression, P16 expression, Ki-67 proliferation, TFF1 expression, PCNA expression)

2.2.2 Secondary Objectives

- Toxicities
- Correlative science and tissue banking

2.3 Outcome Measures

Feasibility: the approach will be considered feasible if more than 50% of the enrolled patients are treated and followed within protocol rules, if collected samples are suitable for studies, and if pathologic changes are detectable when comparing diagnostic and surgical specimens, or treated and untreated specimens. In Group A, patients will be treated with palbociclib alone, providing the opportunity to address if proposing this kind of treatment for these patients is feasible. Obtaining human data and feasibility data would be key for designing efficacy/definitive studies of palbociclib in DCIS.

Pathology: we will perform descriptive analysis of microscopic and molecular changes upon exposure to palbociclib. Biological markers will be tested by immune histochemistry (IHC). Source for comparison will be pretreatment versus post-treatment paired samples. This study will represent an opportunity to describe potential pathological changes triggered by palbociclib as a single agent in DCIS.

Toxicity: will be evaluated by CTCAE. There is no plan to compare Groups A and B regarding efficacy or toxicity. Toxicity will be descriptive for each treatment group, independently.

Correlative science: Will be performed at Lombardi Comprehensive Cancer Center. Preliminary data for this proposal was obtained using a well-established model of DCIS progression with the human MCF-DCIS cell line^{45,47}. Proposed translational components are currently routinely done at LCCC. There is no plan to compare Groups A and B regarding translational changes. Paired samples (pre- and post-systemic therapy) will be compared within the respective Group. **DCIS Sample #1** is the core biopsy

done for diagnosis, **DCIS Sample #2** is collected at definitive surgery; both collected from the same patient (paired).

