3.1.1 Overview of Study Design

This is a feasibility study which will evaluate the pre-operative treatment of DCIS of the breast with palbociclib. Patients with biopsy-proven DCIS are eligible for the study.

There will be 2 independent and unrelated study groups of 12 patients each, for a total of 24 patients:

- (a) Group A, of *male or female* patients treated with palbociclib single agent (n=12);
- (b) Group B, untreated, of *male or female* patients who consented translational studies in blood, as well as diagnostic and definitive surgical specimen, but not the pre-operative treatment with palbociclib (n=12).

Figure 3: Study schema

* Please refer to [Timing of Surgery](#) item below for details on scheduling for Group B.

Patients will be offered participation in the study at the diagnosis of DCIS (confirmed by pathology). Patients could consent biomarker and treatment (Group A) or biomarker-study only (Group B) activities. Once the patient is consented, archival tissue from the diagnostic biopsy will be obtained during screening and used for research in both Groups A and B. Positive Rb by immunohistochemistry in the DCIS component of the lesion will be required for participation on both Groups A and B. Patients consenting study participation will be referred to Medical Oncology clinic and undergo screening. After successful screening, patients enrolled on Group A will be treated preoperatively with palbociclib. **There will be no randomization.** The assignment to Group A or B is based on patient's choice. All patients consenting treatment on Group A will receive palbociclib alone. Since some patients may consent tissue collection, but not preoperative palbociclib treatment, Group B was created to acquire information about contemporary patients receiving biopsy followed by definitive surgery. This approach was first described by Stearns and Davidson⁵².

Choice of histology: a core biopsy showing DCIS-only will not rule out invasive disease. In some instances, invasive disease is found at definitive surgery. Since the proposed treatment will happen between diagnostic biopsy and definitive surgery, it is not practical to exclude from analysis patients

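### Response to palbociclib is judged by core-to-surgery change within Group A, with no planned A-versus-B contrast, so drug effect cannot be separated from specimen type and time since biopsy

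*Combined protocol and SAP*

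**What the plan says.** Section 2.2.1 defines the response objective as "Pathologic changes of breast tissue comparing paired biopsies before and after treatment (core vs definitive surgery) from each patient". Section 6.1 tests change in histologic or molecular parameters with paired t-tests, or with McNemar's test for proportions. It specifies no estimate or test between groups.

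Four paragraphs of section 2.3 bear on the comparison:

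- **Pathology:** the comparison is between pre- and post-treatment pairs, and "This study will represent an opportunity to describe potential pathological changes triggered by palbociclib as a single agent in DCIS".
- **Toxicity:** "There is no plan to compare Groups A and B regarding efficacy or toxicity".
- **Correlative science:** "There is no plan to compare Groups A and B regarding translational changes"; paired samples "will be compared within the respective Group".
- **Feasibility:** one condition is met "if pathologic changes are detectable when comparing diagnostic and surgical specimens, or treated and untreated specimens".

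Section 3.1.1 explains that "Group B was created to acquire information about contemporary patients receiving biopsy followed by definitive surgery". It also states that there is no randomisation: "The assignment to Group A or B is based on patient's choice". Section 4.3.2.2 confirms that Group B contributes both the diagnostic core and surgical material.

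**The concern.** Between the two Group A samples, three things change at once: the patient has taken palbociclib, the tissue has gone from a core to a surgical specimen, and time has passed since the biopsy. Section 3.1.1 itself allows for post-biopsy healing when it sets Group B's surgery window, and Group A tissue has been biopsied too. A one-group paired test measures the sum of these influences.

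Two errors are possible. A specimen or interval effect may be read as drug response, or a real drug effect may be hidden by a non-drug shift in the opposite direction. Section 1.3.2 says the data are to support the design of a larger efficacy study, so either error would carry forward.

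Group B's pairs carry the specimen and time components without the drug, but no planned analysis sets them against Group A's. The feasibility condition does invoke treated against untreated specimens, which conflicts with the two no-comparison sentences and has no method in 6.1. As worded, that condition can also be met by any core-to-surgery change, including one unrelated to the drug.

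**Working it through.** **Inputs.** From section 6.1: 12 patients per group, 12 + 12 = 24 in total, chosen by a pilot-study rule of thumb. There is no power calculation to reproduce, and 6.1 says parameters for the expected change are unavailable. Alpha, SD and effect size are not given. I assume a two-sided 5% level and express every effect in units of the SD of the within-patient change, taken as equal in both groups.

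**Model.** Mean change in A = δ + s_A, and mean change in B = s_B, where δ is the drug effect and s is the shift from specimen type and elapsed time. The Group A test addresses δ + s_A. The contrast A − B addresses δ + (s_A − s_B).

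**Group A paired t-test.** With df = 11, the critical value is 2.201 and the noncentrality is d√12 = 3.464d, where d = δ + s_A.

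| d (SD) | Noncentrality | P(reject) |
|---|---|---|
| 0.3 | 1.04 | 0.158 |
| 0.5 | 1.73 | 0.353 |
| 0.8 | 2.77 | 0.714 |

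- *No drug effect (δ = 0):* these are false attributions to the drug of 16%, 35% and 71%.
- *Masking (δ = 0.8):* detection is 71% with no shift. An opposite shift of 0.3 leaves d = 0.5 and 35%. An opposite shift of 0.5 leaves d = 0.3 and 16%.

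**Binary markers, exact McNemar, n = 12, no drug effect.** If non-drug discordance is 30% one way and 5% the other, the test is significant in 8% of trials. With 50% and 5% it is significant in 42%.

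**Reading two within-group p-values side by side.** With a common shift of 0.5 SD and no drug effect, A is significant and B is not with probability 0.353 × (1 − 0.353) = 0.228. Reporting both groups' tests does not replace a contrast.

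**A-minus-B difference in change, 12 against 12.** With df = 22, the critical value is 2.074 and the noncentrality is d√(12/2) = 2.449d, where d = δ + (s_A − s_B).

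| d (SD) | Noncentrality | P(reject) |
|---|---|---|
| 0.3 | 0.73 | 0.108 |
| 0.5 | 1.22 | 0.216 |
| 0.8 | 1.96 | 0.466 |
| 1.2 | 2.94 | 0.802 |

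- *Equal shifts, no drug effect:* the shift cancels and the rejection rate is 5%. Simulation with 100,000 trials gave 5.0% and 5.1% at common shifts of 0.5 and 0.75 SD.
- *Unequal shifts, no drug effect:* a difference of 0.3 or 0.5 SD gives false rejection of 11% or 22%.
- *Power with equal shifts:* 22% at 0.5 SD, 47% at 0.8 SD and 80% at 1.2 SD.
- *Masking (δ = 0.8):* an opposite difference in shift of 0.3 or 0.5 SD leaves d = 0.5 or 0.3, so detection falls to 22% or 11%.

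**Precision (95% CI half-width).** Within one group: 2.201/√12 = 0.635 SD. Between groups: 2.074 × √(2/12) = 0.847 SD. The ratio is 0.847/0.635 = 1.33.

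**The case against.** The strongest reply is that avoiding the comparison is a deliberate and disclosed choice. Patients choose their group, Group A has extra eligibility criteria (4.1.1, 4.1.2), and 12 against 12 is small. The Pathology paragraph speaks only of an opportunity to describe potential changes, which is weaker than a causal claim. The leading no-comparison sentence sits under Toxicity and the other under Correlative science, a secondary objective. Group B's change may still be described.

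The proposed contrast is also an incomplete cure. Section 3.1.1 estimates at least 18 days from enrolment to surgery in Group A and at most 4 weeks from biopsy, against 5 to 42 days from biopsy in Group B. Early Group B surgeries therefore have no Group A counterpart, and adjusting for days would extrapolate there. Surgery in Group A may be postponed for cytopenias, so the interval can depend on treatment. Section 4.6 replaces patients who are non-compliant or stop treatment. The contrast has its own masking problem, as shown above.

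Most of this stands as a limit on how the contrast may be read. It does not rescue the within-group test, which carries the whole non-drug shift, while the contrast carries only the difference in shifts between groups. The Toxicity sentence names efficacy explicitly, and the Correlative science sentence covers tissue changes. The contradiction with the feasibility condition remains in any case. The descriptive aim lowers the stakes, but 6.1 does plan significance tests.

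**Conclusion.** The concern holds. As planned, a Group A core-to-surgery change cannot be attributed to palbociclib, and section 2.3 contradicts itself on whether treated and untreated specimens will be compared.

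The size is conditional. The documents give no non-drug shift, so the 16% to 71% false-attribution range illustrates shifts of 0.3 to 0.8 SD and is not an estimate for this trial. The contrast holds its 5% level only if the non-drug shift is equal in both groups, which self-selection and unequal intervals make uncertain.

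This is a weakness of the analysis plan, because the untreated pairs are already to be collected, and it is not a sample-size error. It should be fixed. The consequence is limited because the pilot is largely descriptive and ties no decision to a p-value.

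**What to change.** 1. In 2.3, reconcile the two no-comparison sentences with the feasibility condition on treated and untreated specimens.
2. In 6.1, pre-specify for each pathology or IHC marker the mean change in A, the mean change in B, and the A-minus-B difference in change with a 95% CI. Label the difference exploratory and non-randomised.
3. Report baseline marker value and days from biopsy to surgery by group. Adjust for them only as a sensitivity analysis, noting the limited overlap in intervals and the small sample.
4. State that the marker panel is run on Group B's pairs as well.
5. Keep the within-group paired tests as description, and do not attribute Group A change alone to palbociclib.
6. State the limits of the contrast: self-selection, different eligibility, different intervals, and replacement of patients who do not comply or who stop treatment.

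**Cost.** Protocol and SAP wording, plus one estimate per marker. Section 4.1.1 describes Group B as being for the biorepository only, and no Group B marker list is given, so staining up to 24 further specimens (12 pairs) per marker may be needed. Section 3.1.1 presents Group B as a biomarker group, so some of this may already be intended. The price is an interval 33% wider, low power, and a contrast still open to selection. If it is declined, the minimum is to state that Group A change is not attributable to palbociclib alone and to resolve the feasibility wording.

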3. STUDY DESIGN

3.1 Description of Study

[figure not shown]
3.1.1 Overview of Study Design

This is a feasibility study which will evaluate the pre-operative treatment of DCIS of the breast with palbociclib. Patients with biopsy-proven DCIS are eligible for the study.

There will be 2 independent and unrelated study groups of 12 patients each, for a total of 24 patients:

- (a) Group A, of *male or female* patients treated with palbociclib single agent (n=12);
- (b) Group B, untreated, of *male or female* patients who consented translational studies in blood, as well as diagnostic and definitive surgical specimen, but not the pre-operative treatment with palbociclib (n=12).

Figure 3: Study schema

* Please refer to [Timing of Surgery](#) item below for details on scheduling for Group B.

Patients will be offered participation in the study at the diagnosis of DCIS (confirmed by pathology). Patients could consent biomarker and treatment (Group A) or biomarker-study only (Group B) activities. Once the patient is consented, archival tissue from the diagnostic biopsy will be obtained during screening and used for research in both Groups A and B. Positive Rb by immunohistochemistry in the DCIS component of the lesion will be required for participation on both Groups A and B. Patients consenting study participation will be referred to Medical Oncology clinic and undergo screening. After successful screening, patients enrolled on Group A will be treated preoperatively with palbociclib. **There will be no randomization.** The assignment to Group A or B is based on patient's choice. All patients consenting treatment on Group A will receive palbociclib alone. Since some patients may consent tissue collection, but not preoperative palbociclib treatment, Group B was created to acquire information about contemporary patients receiving biopsy followed by definitive surgery. This approach was first described by Stearns and Davidson⁵².

Choice of histology: a core biopsy showing DCIS-only will not rule out invasive disease. In some instances, invasive disease is found at definitive surgery. Since the proposed treatment will happen between diagnostic biopsy and definitive surgery, it is not practical to exclude from analysis patients

that are found to have invasive disease at definitive surgery that was concomitant with DCIS. Information about the invasive component will be collected if present, but the purpose of the current project is to describe palbociclib effects on the DCIS component. Likewise, if other concomitant lesions are detected at final pathology from definitive surgery, i.e. lobular neoplasia, atypical hyperplasia, papilloma, etc, pertinent data will be collected. However, this study will be focused on the effects of palbociclib on the DCIS component of lesions. Since hormonal receptors in DCIS are typically available only at pathologic specimen from definitive surgery, ER or PR status will not be used for patient selection in this feasibility study. Information on ER and PR status will be collected from the pathology report of definitive surgery.

Rb screening: Diagnostic biopsies of participating patients will be tested for Rb expression by immunohistochemistry during trial Screening Phase. The expression of Rb in DCIS lesions is expected in greater than 80% of the cases⁵³. We estimate 30 patients will need to be screened with Rb staining of diagnostic biopsies to complete enrollment. The turnaround time of this test at MedStar Georgetown University Hospital when pathology specimen is located at main laboratory is 48-72hr and therefore considered feasible as screening procedure. This is based on previous extensive experience at our institution with a phase I clinical trial that is ongoing ([NCT01522989](#))⁵⁴. The population will therefore be enriched to increase the likelihood of benefit from this therapy through Rb status evaluation by immunohistochemistry (IHC) at study entry. Rb staining will be considered positive when 1+ or above (in a scale of 0, 1+, 2+ or 3+).

Timing of definitive surgery: All enrolled patients will undergo definitive surgery (mastectomy or lumpectomy).

Group A:

First day of palbociclib treatment will be called Day #1 on study. Last day of palbociclib treatment will be called Study Day #12. Definitive surgery will be performed after end of palbociclib in Group A, on Study Day #15 +/-1. The short period between end of palbociclib and surgery date was selected observing safety and translational data from patients with invasive ductal carcinoma treated with higher dose and longer period of palbociclib in the neoadjuvant setting. A long wash out period without the drug prior to surgery (2-4 weeks) is not desirable since it may be associated with rebound on Ki67 in patients receiving neoadjuvant palbociclib for invasive ductal carcinoma⁵⁵. In 8 patients receiving additional palbociclib 125 mg QD for 12 days until the day prior to surgery, recovery of Ki67 in tissue was diminished⁵⁵. This study also showed that it was safe to proceed with immediate surgery after the palbociclib treatment specified above.

In the current study, the starting date of treatment with Palbociclib for Group A patients will be determined by the surgery date schedule. A maximum period of 4 weeks between initial biopsy and definitive surgery is estimated for patients enrolled to treatment Group A. In case of cytopenias, surgery will be postponed for 7 days (**please refer to session 5.1.3 Management of Specific Adverse Events, for details**). This interval was felt to be acceptable and in line with current practice out of clinical trials. Minimum length of time from enrollment to definitive surgery on treatment Group A is estimated 18 days (Eligibility verification, Rb-testing, Palbociclib dispensation, Palbociclib treatment for 12 days and definitive surgery after stopping treatment).

Group B:

There is no preoperative palbociclib treatment in Group B. Accounting for healing process after diagnostic biopsy, consenting process, Rb screening and to prevent excessive delays since original diagnosis, we recommend that definitive surgery occurs between 5 and 42 days since original diagnostic biopsy.

Collection of tissue at definitive surgery (sample #2): A certified pathologist will be responsible for tissue handling and destination to research. Unfortunately, performing a research-only core at surgery is not felt to be practical in patients with diagnosis of DCIS, since one of the key components of pathologic exam is to rule out invasive component. Therefore, an additional core at surgery is not felt to be safe for patients. Tissue will be collected for translational studies based on certified pathologist examination of material and without compromise of definitive diagnosis. There is a possibility that at definitive surgery invasive lesions are detected. We will describe the same parameters for DCIS lesions and for invasive lesions. Invasive component histologic abnormalities description will be purely exploratory. The focus of this study is DCIS. Pathologist will fill out a form confirming collection of sample for the trial ([Appendix L](#))

Follow up period: Patients will be followed at the postoperative period in the outpatient setting, at which point any additional systemic treatment for DCIS or invasive breast cancer will be discussed. The End of Study visit will occur approximately 2 to 3 weeks after surgery. The Informed Consent form will contain terminology asking patients for permission for the researchers to review the medical chart at 1 year and at 5 years from enrollment to collect additional clinical information about medical history, disease status and treatments.

The study procedures are summarized in [Appendix A](#).

The study schema is presented in [Appendix B](#).

The calendar template for treatment and visits timeline planning based on surgery date for patients enrolled on treatment Group A (Palbociclib) is presented in [Appendix C](#).

The Enrollment Process to Treatment Overview is presented in [Appendix D](#).

